5.4 Research Activities

Pre-screen

Individuals interested in participating in the study can complete the pre-screener questionnaire through the UniSC website, which provides preliminary feedback on the likelihood of a PTSD diagnosis. This pre-screening tool is not a formal assessment but can help guide whether an individual should seek a referral. Individuals may also be directly referred to the study by their GP or psychiatrist if there is a strong indication of a PTSD diagnosis or if a diagnosis is already established.

If PTSD is likely, the individual will be scheduled to have a screening phone call with a Mental Health nurse to further assess their suitability. If PTSD is deemed unlikely, alternative community service options will be suggested. Pre-screen questionnaire examples can be found in Appendix E.

Screen

Once potential participants have been identified, the registered mental health nurse or mental health clinician will complete a screener questionnaire over the phone to ascertain whether the individual potentially meets eligibility criteria. Suitability will be assessed against the inclusion and exclusion criteria, and rating scales such as the PCL-5. If successful, the potential participant will be scheduled to come into the TI/NPRC for an in-person clinical assessment with the research team. All potential participants will be advised that a drug and alcohol screen (urine test) will occur on arrival at T1 baseline and again at T5. Potential participants will be advised that they will not be excluded from the study if a positive result is found during the screen but instead the results will be used as a discussion point to understand their substance use and if this may be problematic with propranolol use. The screen materials will be disposed of immediately and only the results collected and stored. Potential participants will be given the RPIS and PICF via email prior to their scheduled appointment. Potential participants should read the RPIS and PICF and discuss it with family members and/or their support network before attending. Screener questionnaires can be found in Appendix E.

Baseline (T1) (Week 0)

The baseline assessment will take approximately 4 hours in total and includes the following:

- Medical assessment (see Appendix D for example questions)
- Psychological assessment:
 - o Structured clinical interview (Mini international neuropsychiatric interview)
 - o Semi-structured interview

- Pre-assessment self-report questionnaire pack, including demographic questions (see Appendix E for examples questions).

Medical assessment

A medical assessment will be conducted by the study physician onsite to evaluate potential participants' health status. This assessment will screen for any significant medical health concerns (past or present), drug and alcohol use, heart rate variability, comorbid diagnoses, current medication use, and determine if there are any contraindications to the use of propranolol. The assessment will also consider any history of adverse reactions to propranolol, as well as conditions such as asthma, low blood pressure, diabetes, or cardiac concerns. This information will help determine if a potential participant is eligible to safely participate in the study or if they should be referred back to their treating team in the community. For more detailed information, please refer to the physical health assessment in Appendix D.

Pre-treatment self-report questionnaire pack

All potentially eligible participants will be required to complete a series of self-report measures prior to their in-person assessments. Potential participants will be sent a digital link via email for the *pre-treatment self-report questionnaire* pack which will include the following demographic and self-report questionnaires (See Appendix E for full details):

Demographic questions

- Date of birth
- Sex
- Contact details
- Emergency contact information
- Employment status
- Education level
- Current and past medications taken
- Current and past medical history

Self-report questionnaires

- **Peritraumatic distress inventory (PDI):** 13-item scale measures the level of distress experienced by an individual during and shortly after a traumatic event.
- **Peritraumatic dissociative experiences questionnaire (PDEQ):** 13-item self-reporting scale that assesses an individual's emotional reactions at the time of or immediately after a traumatic event.
- **PTSD Checklist for DSM-5 (PCL-5):** 20-item self-report measure that assesses the 20 DSM-5 symptoms of PTSD.
- **The Impact of Events Scale – Revised (IES-R):** 22-item measure of the subjective response to a specific traumatic event in an adult or senior population.
- **Beck Depression Inventory (BDI-I):** 21 item self-report scale designed to measure the negative emotional states of depression.
- **Post-traumatic growth inventory (PTGI):** 21-item scale, measuring the level of posttraumatic growth in persons who have survived a traumatic event.
- **Childhood Trauma Questionnaire (CTQ):** 28 item scale measuring an individual's experiences of child abuse and neglect.
- **International Trauma Questionnaires (ITQ):** 18 item self-report measure focusing on the core features of Post Traumatic Stress Disorder (PTSD) and Complex PTSD (CPTSD). It was developed to be consistent with the organising principles of the ICD-11.
- **WHO Quality of life (WHOQOL-Bref):** An abbreviated 26 items assess quality of life (QOL) within the context of an individual's culture, value systems, personal goals, standards and concerns.
- **Pittsburgh Sleep Quality Index (PSQI):** 11 item self-report measure focusing on sleep quality and habits.

Psycho-diagnostic assessment

The psychological evaluation will involve a comprehensive assessment of the potential participant's mental health through a semi-structured interview and further questionnaires. This will include gathering a detailed psychosocial history, which covers aspects such as the participant's social environment, life experiences, and family history of mental health concerns. Additionally, the evaluation will focus on identifying any current mental health conditions, conducting a thorough diagnostic evaluation, and considering any differential diagnoses. This process ensures that a complete understanding of the potential participant's psychological wellbeing is obtained to support accurate diagnosis. The evaluation will also include the following structured clinician-led interview:

- **Mini international neuropsychiatric interview (MINI):** The MINI is a brief structured diagnostic interview for assessing the major psychiatric disorders in the DSM-5 by a lay interviewer.

If potential participants are deemed medically fit and meet full eligibility criteria following the baseline assessment, they will be enrolled in the study and progress to the next phase of the study (T2). Those who do not meet criteria will be referred back to their treating team and provided community support options.

Please note: Once all the data pertaining to eligibility has been finalised (including a diagnosis of PTSD as assessed by the battery of tests in the psychological assessment protocol), and the results of the assessments having been reviewed and approved by the study team, the 'Eligibility Checklist' is completed, and the participant can be enrolled on the waitlist. Participants will then be given an ID Card stating their unique study ID, name of study, study drug, and study site. Participants will be instructed to keep this ID card on their person at all times, so that in the event of emergency (e.g. hospital admission) their treating staff will be aware of their participation in a drug study.

Pre-treatment assessment (T2) and waitlist

After the baseline assessment is completed, participants will be placed on a 4-week waitlist, during which time additional assessments will be completed:

Biological assessment

Biological assessment will be conducted by a study nurse and consist of a basic physical examination and blood sample collection consisting of:

- Height and weight measurement
- General observations; Blood pressure, pulse rate, pulse oximetry, respiratory rate and temperature measurement.
- Blood collection (~30 ml (2 tablespoons) - 2 x 10 ml K2EDTA tubes and 1 x 10 ml SST tube) by a certified phlebotomist in the pathology-certified room located within the National PTSD Research Centre
- Passive drool saliva collection
- Hair clip

Neuropsychological assessment

Cognitive functioning will be assessed using the Cambridge Neuropsychological Test Automated Battery (CANTAB) at pre-treatment (T2), post-treatment (T3) and follow-up 2 (T5). The CANTAB is a fully automated, self-administered neuropsychological test battery presented on an iPad. Once the participant details have been entered, the majority of instructions are delivered by CANTAB and the participant responds as instructed by the CANTAB. Specific cognitive tests were selected due to their known relationship to deficits in PTSD individual's cognition and functioning:

1. Motor Screening Task (MOT) – assess sensorimotor deficits and lack of comprehension,
2. Reaction Time (RTI) – assess reaction time, movement time and motor and mental response speeds,
3. Spatial Working Memory (SWM) – assess retention and manipulation visuospatial information,
4. Paired Associates Learning (PAL) – assess visual memory and new learning, and
5. Rapid Visual Information Processing (RVP) – assess sustained attention.

Magnetic Resonance Imaging (MRI)

Magnetic Resonance Imaging (MRI) is a highly flexible, non-ionising imaging technique that can produce detailed images of the human body, without the use of radiation. As such, there are no radiation exposure or dosage limitations with MRI. This is beneficial, as individuals can be scanned multiple times with no detrimental effect.

All MRI scans will be conducted at the Nola Thompson Centre of Advanced Imaging, located on the ground floor of the Thompson Institute, UniSC. MRI brain scans will be acquired using a 3-Tesla Siemens (Erlangen, Germany) Skyra scanner, with a 64-channel head and neck coil. MRI scans will be acquired by trained radiographers or experienced MR scientists. Our procedures for collecting MRI brain scans will adhere to the Thompson Institutes' "Working with MRI Guideline". Prior to enrolling in the study, all participants will complete an MRI safety questionnaire to ensure participant safety and eligibility (Appendix J). MRI ineligibility is not exclusionary (i.e., participants who do have MRI contraindications can still be enrolled in the study). For each study visit, the MRI safety questionnaire will be completed and reviewed by the trained radiographer or experienced MR scientists. Each MRI scan session is identical, and the duration of each session will be approximately 60 minutes. The MRI scan protocol will include scans designed to measure neuroanatomical structure, dynamic brain activity, and neurochemistry.

Incidental findings from MRI

Prior to consent, participants are informed within the RPIS and PICF (Appendix A and B), that their MRI brain scan is being conducted for research purposes, and as such, is not clinically valid for diagnosis. Importantly, participants are also informed that our research team is not qualified to provide clinical opinions or medical diagnosis based on their brain scans, and reviewing their scans for that purpose is not within our team's scope of practice. However, if a suspected incidental finding or abnormality is identified by our research team or scan operators, we will adhere to the incidental finding policy indicated within the Working with MRI Guideline. Participants are also given the choice to indicate if they would like to be informed of an incidental finding, should one be identified. In short, if a senior research staff involved in the MRI procedure identifies a suspected incidental abnormality, and participants have consented to being notified of this occurrence, this will be communicated to the participant via a phone call from either the principal investigator or a senior member of the clinical research unit. This is the approved policy put forth by the MRI Operations and Safety committee. Participants will be offered a letter addressed to their GP, with a photo of the scan, and may choose to meet with their GP of their own accord. Participants are informed in the PICF, and again in-person, that the MRI scan is not a medical scan, and that research staff are not qualified to make any diagnoses.

Intervention phase (weeks 1 – 6)

Provided that no contraindications to participation were identified in the T1 or T2 assessments, participants will take part in a 6-week treatment period, consisting of once per week RT sessions. If participants miss more than 3 weeks of RT intervention, they will be excluded from the study. Each RT session will last between 25 and 50 minutes per session. Participants will be on their "treatment as usual" regimen which implies that they will continue to take all their regular medications. The propranolol medication used to conduct RT will be adjunctive (as approved by the study GP regarding possible contraindications). Following each treatment session, participants will provide a saliva sample through passive drool collection.

Post-treatment assessment (T3) (week 7 or 8)

The project lead will coordinate with each participant to attend a session at Week 7 or 8 to collect post-treatment assessment measures. See Table 1 for specific assessments completed during this stage.

Follow up 1 (T4) 1 month

The project lead will coordinate with each participant to attend the follow up 1 telehealth session, which will take 50 minutes. This will involve a clinical interview and psychological measures (PCL-5, IES-R, and BDI-I).

Follow up 2 (T5) 3 month

The project lead will coordinate with each participant to attend the 3 month follow up assessment taking approximately 4 hours in total. See Table 1 for specific assessments completed at this stage.

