5.1 Methodological Approach

In this study, participants will receive manualised (Brunet & Lonergan, 2010) propranolol-based reconsolidation blockade treatment (hereafter called RT) once per week for six weeks in a single treatment arm. Each RT session will be conducted by trained practitioners. Session 1 will last 50 minutes while Sessions 2-6 will last 25 minutes and involve a script recall exercise to activate the specific trauma memory targeted for that session. Participants will be instructed to take the study oral medication (1mg/kg according to ideal weight) 60 minutes with a light snack before each scheduled RT session (i.e., 6 once-a-week doses over 6 weeks). The first dose will be taken on site under supervision of a registered nurse with access to a medical doctor. Subsequent doses will be taken at home before each treatment session. On the day of the first propranolol administration, the research trials

physician (GP) will be on-site to monitor for potential hypotensive events and ensure participant safety. This protocol builds on previous propranolol research and aligns with memory reconsolidation theory principles.

Throughout the study, participants will remain under the care of their existing treating team (i.e. medical practitioner, psychiatrist and/or psychologist), who will oversee any modifications to their existing treatments. RT will be used as an adjunctive treatment, allowing participants to maintain their current psychotropic medications, if any, under their physician's guidance. Any changes in medication will be documented by the study staff. It will be strongly recommended to participants and their treating team to not commence any new mental health treatments during the clinical study.

The primary outcome of the study is a change in PTSD symptomatology, assessed using the battery of psychological assessments (i.e., PCL-5, structured clinical interview) at several time points:

- T1 Baseline assessment (week 0)
- T3 post-treatment assessment (week 7 or 8)
- T5 Follow-up 2 (3 month)

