- Person without a uterus
- Premenarchal

- Premenopausal with permanent infertility due to 1 of the following:
 - o Documented hysterectomy
 - o Documented bilateral salpingectomy
 - o Documented bilateral oophorectomy
- Postmenopausal - A postmenopausal state is defined as no menses for 12 months without an alternative medical cause

Exclusion criteria:

- Complex PTSD
- Significant psychiatric condition: psychosis, bipolar disorder, personality disorder, substance use disorder
- Any contraindication to propranolol as determined by the study physician
- Development of serious, adverse, or unexpected events/reactions during the trial
- Previous allergy or reaction to propranolol, or other beta-adrenergic blocking agent
- Participation in any other clinical study at the time of enrolment, or having received any investigation product within 30 days of the day of enrolment onto the study
- Currently pregnant, breastfeeding or intending to become pregnant during the course of the study.
 - o
- Any other condition that, in the opinion of the investigator, may adversely impact the safety of the participant or the accuracy of the study data

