5.5 Discontinuation and Withdrawal

Participants are free to discontinue their participation in the study at any time, without prejudice to further treatment. Participants who discontinue from the study will always be asked about the reason(s) for their discontinuation and about the presence of any adverse events. If possible, they will be seen and assessed by an

Investigator and complete the withdrawal of informed consent procedure (see Appendix B; PICF). Where participants are not willing to continue any research assessments, they will be considered withdrawn from the study. Adverse events will be followed up until resolution, the adverse event stabilises, or the participant is lost to follow up.

Participant discontinuation criteria

Participants will be discontinued from participating in the study in the following circumstances and, if in need, be referred to their primary medical officer

1. Participants who develop any complications during the study
2. Participants who become too vulnerable or fragile during the study
3. Participants who miss more than 3 weeks of the treatment sessions
4. Participants who do not have a treating team

Discontinuation of parts of this study or the entire study will be considered if new information about reconsolidation therapy becomes known to the researchers.

Escalation procedure

If a participant develops a known (or previously undocumented) adverse reaction to the treatment during the study, clinical and research staff will refer to the *Recognising and Responding to Physiological deterioration SOP* which will include some or all of the following:

- Appropriate and timely medical care is provided by trained and qualified staff. If required, the emergency services (Queensland Ambulance Services – QSA) and UniSC security are contacted immediately.
- Attending registered nurse will monitor physiological signs and symptoms on initial session.
- If the ambulance service is not required, the participant will be referred for consultation with their GP and their participation from the study will be withdrawn.
- If the ambulance service is required for immediate medical admission, the clinical and research staff will supply relevant patient information to assist with participant treatment and monitoring.

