5.10 Data Management and analysis

Once completed, screening for the total number of completed surveys will take place and we will ensure no personal details (names, contact details etc) are associated with the survey information. All data collected will be stored in line with the UniSC Research Data Management Procedures.

A unique code will be generated for each participant enrolled in the study to de-identify data. The information for linking unique codes to participant contact information will be made accessible to necessary project staff for the purposes of scheduling assessments. All electronic data will be stored securely on computers at the TI/NPRC or on secure research specific databases. Only researchers will have access to the data and other research documents. The computers will be secured by usernames and passwords and protected from external access. Hard copy documents, material, and data will be kept in a locked filing cabinet, inside a locked office. All paper records will be securely converted to pdf files to mitigate the risk of data loss through an emergency (e.g. fire or flood).

Re-identifiable data (using the unique code identifiers) will be exported from Qualtrics to IBM SPSS for analysis. Statistical analyses will include generalised linear models (GLMs), analysis of the relative change index and frequentist statistics. A significance level of $p < .05$ (two-sided test) will be utilised where required. Data will be inspected for outliers and any spurious data will be corrected or removed prior to analysis. A detailed data analysis plan will be constructed by a statistician including the research questions and variables included. Missing data will be examined for missingness patterns. If the data is missing at random or completely at random, data imputation strategies may be employed in order to protect the integrity of this longitudinal sample and statistical power. Data will be analysed using descriptive, bivariate, and multivariate statistics using intent-to-treat analyses.

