Participants are free to withdraw consent at any time, for any reason. Any biospecimen material remaining at the time of withdrawal will be destroyed as per waste disposal guidelines. Any data generated prior to the withdrawal of consent that is identifiable will be destroyed/deleted. However, data that has been deidentified and aggregated for analysis prior to withdrawal of consent cannot be reidentified and removed at this point, so that data will remain within the analysis in an unidentifiable manner. There are no financial or personal interests to be gained by participants in this study regarding their biospecimens. There are no commercial applications expected from this research.

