RC_10	Participant does not attend or is late for allocated assessment procedure	Various reasons outside TI control including failure to attend, not wanting to attend appointment, bad traffic, personal factors	Researchers and rooms booked and no longer required, reschedule required, or loss of data for that time point if unable to reschedule	Research Risk	Moderate	Likely	Medium	
 A protocol will be developed for managing cancellations including actions to take when a participant misses an appointment. Contact participant to check in and reschedule appointment. Participant will continue to be invited to future assessments unless they request to be withdrawn from the study or are outside of the assessment timeframe outlined in the project protocol Participants go through a screening process prior to the start of the study 	Administrative	Effective	Director, Thompson Institute	Manager, Clinical Programs	Moderate	Unlikely	Medium	
RC_11	Access to restricted drugs is compromised	Lack of security, processes or staff error	Medico-legal implications, inability to deliver treatment/research medication, loss of control of restricted substance, legal implications, require contact to police	Research Risk	Moderate	Possible	Medium	
 All Scheduled medications stored in accordance with the Medicines and Poisons Act 2019 (Queensland) the Medicines and Poisons Regulation 2021 (Queensland), and the Thompson Institute Substance Management Plan Regulated Medicines. A drug register will be maintained and regular audits of compliance regulations will be conducted in accordance with the Thompson Institute Substance Management Plan Regulated Poisons, Queensland legislation and regulations. The register will be stored in accordance with UnISC data safety policy and requirements of the Information Privacy Act 2009 - Queensland legislation. Any unused Investigational Product drug that is on-site at the end of the trial will be returned to the dispensing pharmacy for disposal. 	Administrative	Effective	Director, Thompson Institute	Manager, Clinical Programs	Moderate	Possible	Medium	

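### Participants are removed from the study, not only from treatment, for missed sessions, reactions or deterioration, with no outcomes provided afterwards; this conflicts with the stated intent-to-treat analysis

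*Protocol*

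**What the plan says.** The design gives reconsolidation treatment (RT) "once per week for six weeks in a single treatment arm" (section 5.1). The primary outcome is change in PTSD symptoms on the PCL-5 and structured interview at T1, T3 and T5.

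Several rules remove people after enrolment:

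- Section 5.4, intervention phase: "If participants miss more than 3 weeks of RT intervention, they will be excluded from the study". Section 5.5 repeats this as a discontinuation criterion.
- Section 5.5, discontinuation criteria: "Participants who develop any complications during the study". A further criterion covers those who become too fragile. Both are discontinued from the study.
- Section 5.5, escalation procedure: for an adverse reaction that does not need an ambulance, one listed step is GP referral, and "their participation from the study will be withdrawn".
- Section 5.7: participants who pose an imminent risk are referred and withdrawn from the study.
- Section 5.2, exclusion criteria: "Development of serious, adverse, or unexpected events/reactions during the trial".

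Section 5.5 defines a withdrawn participant as one who takes no further part at all. On analysis, section 5.10 says: "Data will be analysed using descriptive, bivariate, and multivariate statistics using intent-to-treat analyses". It allows imputation if data are missing at random or completely at random, and makes no provision for data missing for reasons tied to the unseen outcome.

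**The concern.** An intent-to-treat analysis needs outcomes from people who stop treatment. The rules above end study participation for reasons that can be linked to outcome, and the protocol provides no assessment afterwards. With one arm, the result is the mean change itself, and there is no control group subject to the same attrition.

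Section 5.11 lists sleep disturbance and nightmares among the common reactions to propranolol, and section 4.1 lists nightmares and poor sleep as PTSD symptoms. Removal for a reaction could therefore select on the outcome. Section 5.11 adds that such reactions were reported with prolonged daily use, whereas this trial gives six weekly doses, so the overlap may be small.

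The exclusion criterion is a separate fault. Section 5.4 completes eligibility before the waitlist and before any dose, so an event during the trial cannot be an eligibility condition. Left in that list, it could be used to declare a treated participant ineligible after the fact.

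**Working it through.** The protocol gives a target of 150 (section 5.2) and a two-sided 5% level (section 5.10), but no effect size, standard deviation or dropout rate. There is no figure of its own to reproduce, so the finding rests first on the text.

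**Step 1: the passages side by side.**

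| Question | What the protocol says |
|---|---|
| Does stopping RT end study participation? | Yes for missed sessions (5.4, 5.5), complications and fragility (5.5), and imminent risk (5.7). Possibly for a reaction not needing an ambulance (5.5). |
| Is discontinued the same as withdrawn? | Unclear. Section 5.5 lists them separately and calls those unwilling to continue any assessment withdrawn, which hints that discontinuation may stop short of that. |
| Are T3 to T5 outcomes collected after removal? | No section says so. |
| Who is analysed? | Intent-to-treat (5.10). |
| How are missing outcomes handled? | Optional imputation, only if missing at random or completely at random (5.10). |

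Followed as written, the rules leave the intent-to-treat analysis without outcomes for the people they remove.

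**Step 2: illustrative size in points.** Assumed values, not protocol figures: retained participants improve by 15 points, a share w is removed, and those removed worsen by x points.

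Mean over all participants = 15(1 − w) − xw. Overstatement = 15 / (that mean) − 1.

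| w | x = 0: mean | overstatement | x = 5: mean | overstatement |
|---|---|---|---|---|
| 10% | 13.5 | 11% | 13.0 | 15% |
| 20% | 12.0 | 25% | 11.0 | 36% |
| 30% | 10.5 | 43% | 9.0 | 67% |

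**Step 3: illustrative effect on the test.** Work in standard deviations (SD) of individual change. A share f is removed, and those removed do g SD worse than those retained. The true mean change over all 150 is set to zero.

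Bias = f × g; n = 150(1 − f); retained SD = √(1 − f(1 − f)g²). The chance of a significant benefit is 1 − Φ(1.96 − bias × √n / SD).

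For f = 0.10 and g = 1: bias = 0.10, n = 135, SD = √0.91 = 0.954, and 0.10 × √135 / 0.954 = 1.218. The chance is 1 − Φ(0.742) = 0.23, against a nominal 0.025.

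| f | g = 0.5 | g = 1.0 | g = 1.5 |
|---|---|---|---|
| 5% | 0.05 | 0.09 | 0.16 |
| 10% | 0.09 | 0.23 | 0.50 |
| 20% | 0.20 | 0.67 | 0.98 |

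If g = 0 there is no bias. If 10% are removed and they did 0.5 SD better, the bias is −0.05 SD, against benefit. In a simulation of 20,000 runs, analysing all 150 kept the rate at about 0.025.

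**The case against.** The strongest reply is that the protocol never says that data from removed participants are dropped. Section 5.10 leaves detail to a statistician's analysis plan that is not shown, and definitions of analysis sets belong there. That stands: a reader might infer that a completer analysis is planned, and the text does not support it. But an analysis plan cannot recover T3 and T5 assessments that were never made, and whether they are made is a protocol matter.

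Other stronger readings also fail:

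- *Any adverse reaction ends participation.* The escalation steps are offered as a list from which some or all may apply, and the withdrawal step covers only cases not needing an ambulance.
- *Those removed did worst.* This is likely for deterioration, but a drop in blood pressure need not track PTSD outcome, and some people may skip sessions because they feel better.
- *Imputation under missing at random cannot help at all.* The design table lists the IES-R during the treatment weeks, so some deterioration before removal may be observed. The course after removal is not.
- *Adverse events drop out of the safety denominator.* Section 5.5 asks those who discontinue about adverse events and follows the events up, and Appendix I records all of them on the case report form.
- *The risk register already promises continued assessment.* Item RC_10 (Appendix L) says "Participant will continue to be invited to future assessments unless they request to be withdrawn from the study", but it concerns missed or late assessment appointments, and the sentence goes on to except people outside the assessment timeframe. It does not cover people removed for reactions or fragility.
- *Coded data are destroyed.* On consent withdrawal, section 5.10 says "Any data generated prior to the withdrawal of consent that is identifiable will be destroyed/deleted". It says identifiable data, in a passage largely about biospecimens, and the design table treats identifiable and re-identifiable as separate categories.

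One narrower worry remains on the last item. Section 5.5 has people who discontinue go through the consent-withdrawal procedure where possible, so a removal decided by the study team could be handled as revoked consent.

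**Conclusion.** The point holds on the text. The protocol removes participants from the study for reasons that can be tied to outcome, provides no later outcomes for them, places a post-treatment event among the eligibility criteria, and promises intent-to-treat with a missing-data provision limited to random missingness. Section 5.5 leaves open whether discontinuation ends assessment, so part of the fault is ambiguity.

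Bias towards benefit is the expected direction for removal because of reactions or deterioration. For missed sessions it is plausible but not certain. The overstatement of 11% to 43% assumes a 15-point improvement, 10% to 30% removed with zero change, and an estimate from retained participants only. None of these comes from the protocol. The test results in Step 3 are equally assumption-bound and isolate selection: a single-arm pre-post change also contains natural recovery and regression to the mean, which better follow-up does not remove.

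This should be fixed in the protocol, because missing T3 and T5 outcomes cannot be collected later.

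**What to change.** Leave the clinical stopping rules to the investigators, and reconcile sections 5.2, 5.4, 5.5 and 5.7 so that they agree on what each rule ends. Then:

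1. Define stopping RT and leaving the study as separate events.
2. Move the on-trial adverse-event line out of the exclusion criteria.
3. State that participants who stop RT are still invited to the PCL-5 at T3, T4 and T5, and to the interview where feasible, unless they revoke consent or the principal investigator judges further contact not in their interest. Record which exception applied.
4. Keep all enrolled participants in the intent-to-treat set and everyone dosed in the safety set. Enrolment precedes the four-week waitlist, so the two sets differ.
5. Add a sensitivity analysis for outcomes not missing at random, for example one that assigns those removed no change or a stated worsening.
6. Clarify that discontinuation by the study team does not trigger the consent-withdrawal procedure in section 5.5 or the related deletion of data in section 5.10.

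The cost is amendment wording and a few extra questionnaires. These already run through Qualtrics (section 5.9), T4 is already by telehealth, and contact is already kept for adverse-event follow-up. The mean change may come out less favourable.
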